3.2 STUDY ENDPOINT

In this Pilot study four (4) domains of interest have been designated. The four (4) domains are:

1. Patient Safety: Safety Endpoint Measures include adverse events, laboratory safety parameters, vital signs, EKG, ventilation status and hemodynamic variables.
2. Clinical Efficacy: The Primary Clinical Efficacy Endpoint Measure is in-hospital; 28 and 60-day all-cause mortality. Time to renal recovery and necessity for chronic dialysis up to day 60 will also be determined. Additional efficacy endpoints include time to intensive care unit (ICU) discharge, and time to hospital discharge.
3. Device Integrity and Performance: The Endpoint Measure is SCD use without failure. This measure will help assess the integrity and performance of the SCD device.
4. SCD Mode of Action: Exploratory Endpoint Measures will include inflammatory cytokines, cell activation parameters and biomarkers at clinical sites with this capability.

Endpoints are defined as:

ALL-CAUSE MORTALITY:

All-cause mortality is defined as in-hospital, 28-day and 60-day all-cause mortality.

DIALYSIS DEPENDANCY AT DAY 60:

Dialysis dependency at day 60 is defined as patient not receiving any form of intermittent or continuous renal replacement therapy at or within 3 days of 60 days post enrollment in the study with no plans for additional intermittent or continuous renal replacement therapy.

PATIENT SAFETY:

Adverse events, laboratory safety parameters, vital signs, EKG, ventilation status and hemodynamic variables.

DURATION OF RENAL SUPPORT:

The duration of renal support will be defined as the numbers of days from the initiation of renal replacement therapy (start of observation period) to final dialysis treatment. Duration of renal support will be censored if the patient is still dialysis dependent at the time of death or are dependent at day 60.

RECOVERY OF RENAL FUNCTION:

Recovery of renal function will be defined as lack of need for continuous dialysis support on day 28, and will be classified as yes or no at day 28.

Subjects who were alive at day 28 will be included in the analysis.

Patients who remain dialysis dependent at study completion (day 60) or time of death will be categorized as having no recovery of renal function.

ASSESSMENT OF DEVICE INTEGRITY AND PERFORMANCE

Criteria for assessment of device integrity and performance include:

- Significant Clotting within the Device as assessed by visual inspection

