5.2 INCLUSION CRITERIA

1. The patient's parent or legal representative has provided informed consent.
2. Must be receiving medical care in an intensive care unit (e.g., PICU, CICU).
3. Age less than 18 years.
4. Body weight between ≥ 10 and ≤ 20 kg
5. Intent to receive full supportive care through aggressive management utilizing all available therapies for a minimum of 96 hours.
6. Clinical diagnosis of AKI requiring CRRT. AKI is defined as acute kidney injury with any one of the following:
 - Increase in SCr by ≥ 0.3 mg/dL (≥ 26.5 μ mol/L) within 48 hours or;
 - Increase in SCr to ≥ 1.5 times baseline, which is known or presumed to have occurred within the prior 7 days or;
 - Urine volume <0.5 ml/kg/h for 6 hours
7. At least one non-renal organ failure (defined as receiving mechanical ventilation or at least one vasoactive medication to treat hypotension) OR presence (proven or suspected) of sepsis. Sepsis is defined as at least two of the following criteria in the setting of a probable or documented infection^[29]:

Age	1mo-1yr	2-5 yr	6-12 yr	13-17 yr
Tachypnea (breaths/min) or mechanical ventilation not related to underlying neuromuscular disease of the receipt of general anesthesia	> 49	> 22	> 18	> 14
Tachycardia (beats/min)	> 150	> 140	> 130	> 110
Bradycardia if <1 yr (beats/min)	< 109			
Hyper or Hypothermia			> 38.5°C or < 36°C	
WBC ($\times 10^3/\text{mm}^3$)	> 17.5 or < 5	> 15.5 or < 6	> 13.5 or < 4.5	> 11 or < 4.5

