If a patient develops hypotension or experiences worsening hypotension during CRRT/SCD initiation (defined as a > 10 mmHg decrease in mean arterial pressure (MAP) during the first 15 minutes of CRRT initiation or integration of the SCD into the circuit), the patient, depending on the site PI's judgement, will receive a either a 10 ml/kg crystalloid bolus over 10 minutes or vasoactive medications will either have their dose increased (if already prescribed) or will be initiated. Each center will select the vasoactive medication that is best suited for the clinical indication.

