6.2.4 Concomitant Medications

Since clearance or adsorption of medications have not been completely studied with SCD therapy, dosing of concomitant medications as per other extracorporeal therapies should be employed and evaluated during SCD treatment. In this regard:

- Subjects are permitted to take prescribed medications only.
- Continuously administered intravenous medications should be administered without interruption during SCD therapy
- Essential oral medications should be administered without adjustment of their dosing schedule
- Emergent intermittent intravenous and oral medications will be administered when required, without regard to the timing of SCD therapy
- For antibiotics, subjects will receive standard of care anti-infective dosing according to published schedules adjusted for CRRT [30]. Antibiotic serum levels will also be measured as per standard of care guidelines to ensure effective dosing and avoidance of toxicity.
- For vasopressors, dose adjustments will be made to achieve targeted mean arterial pressure.

A list of critical medications is listed in **Appendix C**. The clinical investigators will be alerted to evaluate dosing schedules for these medications carefully for potential adjustments to achieve desired effects during SCD therapy.

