6.4 BASELINE PERIOD

The Baseline Period begins at enrollment and ends at the start of the SCD Treatment Period (when the subject starts treatment). The following information will be recorded as close to the start of the SCD Treatment Period as possible. Data from standard of care tests may be used as baseline data, as long as it is captured within the time frames noted.

- **Demographic Data**
 - a) Date of birth
 - b) Gender
 - c) Race/ethnicity
- **Hospitalization Data**
 - a) Hospital Admission Date
 - b) Hospital Admission Diagnosis
 - c) ICU Admission Date
 - d) ICU Admission Diagnosis
 - e) Medical History
- **Vital Signs/Physical Assessment (within 12 hours prior to the start of SCD Treatment Period unless otherwise indicated)**
 - Temperature
 - Blood Pressure and heart rate
 - Body weight at ICU admission
 - PRISM II Score
 - Physical Exam
 - Urine Output (previous 24 hours)
 - ICU percent fluid overload at CRRT initiation (Defined as [(Fluid In (liters) – Fluid Out (liters))/ICU admission weight (kg)] x 100% where Fluid In and Fluid Out are calculated from ICU admission to CRRT initiation.
- **Clinical Laboratory Tests (within 12 hours prior to the start of SCD Treatment Period)**
 - CBC with differential
 - BUN/Creatinine
 - Na, K, Cl, HCO₃, Ca, Mg, Ionized Ca, PO₄
 - ALT, AST, Bilirubin, ALP, Total Protein, Albumin, Glucose
- **Respiratory**
 - Status – Ventilator support (yes/no; date of intubation)
 - If on Vent: FiO₂
 - If on Vent with an arterial line: Arterial Blood Gas (12 hours prior to start of SCD Treatment Period)
 - If on Vent without an arterial line: Arterial Blood Gas (if available within 12 hours of start of Observation Period per standard of care)
 - ECMO Status (yes/no; date of cannulation)
- **Blood for Research**
 - Blood sample should be collected within 6 hours before the start of the SCD Treatment Period

- Blood sample will be sent to an outside laboratory for testing of biomarkers. The research laboratory is Innovative BioTherapies located at [name].
- **Other (Event-driven)**
 - Acknowledgement (yes/no) to critical medications, vasopressors, and blood products administered to the patient in the 24 hours prior to start of SCD Treatment Period
 - Adverse Events occurring since enrollment
 - Microbiology/culture data (within the last 72 hr.)

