Therapy Initiation	Q 1 hr \pm 30min. until post filter iCa level <0.40 mmol/L; for two consecutive measurements within the first 12 hours of SCD then Q 6hr \pm 1hr.
After any Calcium or Citrate rate change	Q 1 hr \pm 30min. until post filter iCa level <0.40 mmol/L; then Q 6hr \pm 1hr.
After any Interruption: Recirculation, Procedure, Restart	Q 1 hr \pm 30min. until post filter iCa level <0.40 mmol/L; then Q 6hr \pm 1hr.

- **SCD Performance (Start at hour 0)**
 - SCD █ performance (event driven)
 - SCD and SCD Blood Tubing Set Change every 24 hour (\pm 4 hours)
- **Other (Event Driven)**
 - Acknowledgement (yes/no) to critical medications, vasopressors, and blood products administered to the patient
 - Adverse Events
 - Diagnostic/Therapeutic Procedures
 - Microbiology/culture data

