The Prospective Pediatric CRRT (ppCRRT) database will be used as a control for the CRRT treatment related factors including: patient age, gender, primary cause of AKI, total treatment duration, CRRT modality (CVVH, CVVHD, CVVHDF), CRRT small solute clearance (ml/1.73m²/hour), baseline estimated GFR (using the original Schwartz formula, which was used in the ppCRRT), urine output in the 24 hours prior to CRRT initiation (ml/kg/hour), percent fluid overload at CRRT initiation based on admission ICU weight, vasoactive medication number at time of CRRT initiation and mean airway pressure at CRRT initiation.

An additional analysis will also evaluate patients who have achieved targeted iCa levels during 90% of treatment time and those who do not.

In summary this protocol meets all criteria necessary for clinical scientific inquiry related to a test of hypothesis in a well monitored environment focused on subject safety during the conduct of the study. Basic statistics will be performed on the data sets along with historical data comparisons and subjected to subset analysis where appropriate. The results will help to guide the design of a future pivotal study of this device.

The rational for therapy, study objectives and endpoints, design, inclusion and exclusion criteria are explicitly defined. Subject safety parameters are well documented including safety reporting, safety observations and assays, procedures for subject withdrawal and study discontinuation criteria along with monitoring device integrity and performance. Lastly, a review of all prior SCD human study safety data is included in the protocol for full disclosure to study investigators and the informed consent document includes a full description of all known and potential risks of the device treatment.

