APPENDIX C – CRITICAL MEDICATION LIST

The following is a list of medication categories (with examples) to be acknowledged (yes/no) in the Case Report Forms if administered to the patient during the SCD-PED-02 Clinical Trial (starting at 24 hours prior to SCD Treatment until 240 hours of treatment or ICU discharge, whichever comes first). In addition, antibacterial use is captured during the Post SCD follow-up period.

ANTIBACTERIALS FOR SYSTEMIC USE

- Ampicillin
- Azithromycin
- Aztreonam
- Bactrim (Trimethoprim/ Sulfamethoxazole)
- Cefadroxil
- Cefalexin
- Cefazolin
- Cefazolin sodium
- Cefepime
- Cefepime hydrochloride
- Cefoxitin
- Ceftazidime
- Ciprofloxacin
- Ciprofloxacin hydrochloride
- Clindamycin
- Daptomycin
- Doripenem
- Erythromycin
- Gentamicin
- Levofloxacin
- Linezolid
- Meropenem
- Metronidazole
- Moxifloxacin
- Nafcillin
- Piperacillin
- Piperacillin-tazobactam
- Synercid (Quinupristin/ Dalfopristin)
- Tigecycline
- Tobramycin
- Vancomycin

ANTIMYCOTICS FOR SYSTEMIC USE

- Amphotericin B liposome
- Caspofungin
- Fluconazole
- Micafungin

ANTITHROMBOTIC AGENTS

- Acetylsalicylic acid
- Argatroban
- Bivalirudin
- Clopidogrel
- Drotrecogin alfa
- Enoxaparin
- Enoxaparin sodium
- Heparin
- Warfarin sodium

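### Vasopressors are adjusted to a MAP target but the text asks only for a yes/no record, so a rise in vasopressor need on SCD could be partly masked

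*Combined protocol and SAP*

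**What the plan says.** Section 3.2 defines the patient-safety endpoint measures as "adverse events, laboratory safety parameters, vital signs, EKG, ventilation status and hemodynamic variables". Safety is the primary objective (Section 3.1).

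Blood pressure is actively supported. Section 6.2.4 states: "For vasopressors, dose adjustments will be made to achieve targeted mean arterial pressure". Section 6.2.2 covers a MAP fall of more than 10 mmHg in the first 15 minutes of CRRT initiation or SCD integration. At the site investigator's judgement the child receives a crystalloid bolus, or "vasoactive medications will either have their dose increased (if already prescribed) or will be initiated".

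The record of that support is thin:

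- **Baseline (Section 6.4):** "Acknowledgement (yes/no) to critical medications, vasopressors, and blood products administered to the patient in the 24 hours prior to start of SCD Treatment Period".
- **SCD treatment (Section 6.5):** "Acknowledgement (yes/no) to critical medications, vasopressors, and blood products administered to the patient".
- **After SCD (Section 6.6.1):** no vasopressor item is listed, although the schedule in Section 6.3 has a row for vasopressors administered that runs into this period.
- **Registry comparison (Section 12):** "vasoactive medication number at time of CRRT initiation and mean airway pressure at CRRT initiation". This is a count of drugs at one time point.

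No dose, vasoactive score, or analysis of MAP alongside vasoactive support is specified.

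**The concern.** When a drug is titrated to hold blood pressure at a target, information about hemodynamic deterioration moves from the pressure to the drug dose. If the dose is not a data item, part of that information is lost. Taking blood pressure more often would not recover it.

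The protocol gives its own reasons to watch for this. Section 9.1 lists hypotension among the events anticipated when SCD is added to CRRT. Section 6.2.2 notes that priming can dilute vasoactive drugs. Section 6.2.4 says drug clearance and adsorption with SCD are incompletely studied and asks that dosing be evaluated during treatment, which a yes/no item cannot do. For other organ support the protocol does ask for intensity: ventilator settings and FiO2, and CRRT flow and infusion rates (Sections 6.3 and 6.5).

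At stake is whether the safety report could understate a rise in vasopressor need. With at most 10 children and no control arm, each such event carries weight.

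**Working it through.** The plan states no power, effect size or event rate for this endpoint, so there is no figure to reproduce. The check has two parts.

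**1. What the two recorded fields can show, if titration restores the target MAP**

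| Child at SCD start | Change on SCD | Blood pressure | Vasopressor flag |
|---|---|---|---|
| Not on a vasopressor | Vasopressor started | Unchanged | No to yes: visible |
| On a vasopressor | Rate raised or second agent added | Unchanged | Yes to yes: not visible |

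The baseline flag covers the previous 24 hours. A child weaned within that window and restarted on SCD also reads yes to yes.

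**2. Illustration of size**

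Inputs:

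- n = 10, the maximum enrolment (Section 5.1).
- h = share of children whose vasopressor need rises on SCD. Assumed: 30%, with a range of 20% to 50%.
- q = share whose baseline flag is already yes. Assumed: 50% to 90%. The documents give no figure.
- h and q are taken as independent, children as independent, and MAP as restored to target.

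Formulas:

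- Expected escalations = n × h
- Visible in the flag = n × h × (1 − q)
- Masked = n × h × q
- P(at least one visible in the flag) = 1 − [1 − h(1 − q)]^10
- P(at least one visible if dose is recorded) = 1 − (1 − h)^10

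With h = 30%, 10 × 0.30 = 3 escalations are expected:

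| q | Visible | Masked | P(at least one visible), flag | P(at least one visible), dose |
|---|---|---|---|---|
| 50% | 1.5 | 1.5 | 1 − 0.85^10 = 0.80 | 1 − 0.70^10 = 0.97 |
| 70% | 0.9 | 2.1 | 1 − 0.91^10 = 0.61 | 0.97 |
| 90% | 0.3 | 2.7 | 1 − 0.97^10 = 0.26 | 0.97 |

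Over the whole assumed range, the flag gives from 1 − 0.98^10 = 0.18 (h = 20%, q = 90%) to 1 − 0.75^10 = 0.94 (h = 50%, q = 50%). Recorded dose gives from 1 − 0.80^10 = 0.89 to 1 − 0.50^10 = 0.999.

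These are chances that an escalation appears in the vasopressor data. They are not chances of attributing it to SCD, and they leave out adverse event reports.

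**The case against.** A reader might infer that any hemodynamic harm of SCD would be corrected away and reported as no change. The documents do not support that, for these reasons:

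- **Adverse events are a separate channel.** Section 9.1 counts anything that first appears or worsens, whether or not related, and names hypotension. Section 9.7 says expected ICU signs are still reportable if they meet the definition. Section 9.6 grades events by the intervention needed, Section 9.5 requires a causality assessment, and the DSMB meets at least quarterly (Section 11).
- **The Section 6.2.2 response follows a fall that has already been observed**, so it is not hidden from the clinician.
- **Other fields can move.** New starts change the flag, and boluses should enter the daily fluid balance.

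This stands against the absolute reading but does not close the gap. No text requires a Section 6.2.2 MAP fall, or a dose rise that prevents hypotension, to be logged as an adverse event. The moderate grade in Section 9.6.2 cites a new treatment, which a higher rate of an existing drug may not meet. Daily fluid balance does not isolate a bolus given at SCD integration.

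A reader might also infer that the case report form holds only yes/no. That cannot be confirmed. The form is not among the documents, the schedule row states no format, and the Section 12 drug count goes beyond yes/no, though at one time point only. Appendix C says its medication categories are "to be acknowledged (yes/no) in the Case Report Forms if administered to the patient", but the categories shown do not include vasopressors.

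Nor do the documents show that most children enter on a vasopressor. The organ-failure criterion, "receiving mechanical ventilation or at least one vasoactive medication to treat hypotension", can be met by ventilation alone, and sepsis is a further alternative.

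Finally, a dose record would not isolate a device effect. CRRT initiation itself alters hemodynamics (Section 6.2.2), SCD may start together with CRRT (Section 6.5), and there is no concurrent control. That limits interpretation, but it is not a reason to leave the dose unrecorded.

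**Conclusion.** The point holds as partial masking. In a child already on a vasopressor, a dose increase that keeps MAP at target leaves no trace in either the blood pressure or the yes/no field described in the text. In other children a new start is visible. Hypotension reported as an adverse event would also show, but such reporting is not tied to a dose rise or to the Section 6.2.2 fall.

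The size depends on two quantities the documents do not give. Under the assumed 30% with a rise in need and 50% to 90% already on a vasopressor, half to nine-tenths of escalations would be missed by the flag. The chance of seeing at least one is 0.80 to 0.26, against 0.97 with dose recorded. If need rises more often in children already on a vasopressor, the flag shows less than this; if less often, more. If the case report form already collects agent and rate, the gap is in the protocol text and the planned reporting only.

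**What to change.** Change data capture and reporting only, with no change to clinical management:

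1. In Sections 6.4 and 6.5, replace the yes/no vasopressor item with each agent and its infusion rate. Record these with MAP at baseline, just before and after SCD start and each SCD change, and once daily.
2. Record any fluid bolus or vasoactive change given under Section 6.2.2, with its time.
3. Reconcile Section 6.6.1, which lists no vasopressor item, with the vasopressor row of the Section 6.3 schedule.
4. Report MAP together with a summary of vasoactive dose, descriptively. State that a single-arm comparison cannot separate SCD from CRRT or the underlying illness.

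Cost: data entry from the ICU record, with no new procedure. At most this is about 1 baseline + 10 treatment-day + 5 post-SCD-day records, plus 2 × 10 around SCD start and the scheduled changes. That makes roughly 36 time points for a child who completes all ten treatments and the full post-SCD period, and fewer for others. The burden is modest for up to 10 children.

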6.3 SCD SCHEDULE OF EVENTS

	Pre-SCD	SCD TREATMENT PERIOD ¹										POST SCD PERIOD ²			Day 28 ³	Day 60 ³
		Hr 0-24	Hr 24-48	Hr 48-72	Hr 72-96	Hr 96-120	Hr 120-144	Hr 144-168	Hr 168-192	Hr 192-216	Hr 216-240	Hr 0-24	Hr 24-48	Hr 48-72	Hr 72-96	Hr 96-120
Vital Signs / Physical Assessment																
ICU Admission Weight	X															
Temperature, BP, Heart Rate	X	X	X	X	X	X	X	X	X	X	X	X	X	X	X	X
Daily Fluid Balance and Urine Output	X	X	X	X	X	X	X	X	X	X	X	X	X	X	X	X
Blood Product Administration	X	X	X	X	X	X	X	X	X	X	X	X	X	X	X	X
Critical Medications	X	X	X	X	X	X	X	X	X	X	X	X	X	X	X	X
Physical Exam by Investigator	X											X				
PRISM II Score	X															
Sepsis Assessment	X															
Fluid Overload at SCD Initiation	X															
Microbiology / Culture Data	X	X	X	X	X	X	X	X	X	X	X	X	X	X	X	X
Concomitant Treatments or Procedures	X	X	X	X	X	X	X	X	X	X	X	X	X	X	X	X
Laboratory Testing																
CBC with differential	X	X	X	X	X	X	X	X	X	X	X	X				
Creatinine	X	X	X	X	X	X	X	X	X	X	X	X	X		X	X
BUN, Na, K, Cl, HCO ₃ , Ca, Mg, PO ₄ , iCa	X	X	X	X	X	X	X	X	X	X	X	X	X			
ALT, AST, Bilirubin, ALP, TP, Albumin, Glucose	X	X	X	X	X	X	X	X	X	X	X					
Blood for Research Biomarkers ⁴	X		X		X		X		X		X				X	
Cardiorespiratory Assessment																
Ventilator Use and Settings	X	X	X	X	X	X	X	X	X	X	X	X	X	X	X	X
Arterial Blood Gas ⁸	X	X	X	X	X	X	X	X	X	X	X	X	X			
Vasopressors Administered	X	X	X	X	X	X	X	X	X	X	X	X	X	X	X	X
ECMO	X	X	X	X	X	X	X	X	X	X	X	X	X	X	X	X
Renal Replacement and SCD																
Post Filter iCa	X ⁵	X ^{6,7}	X ⁷													
SCD Filter Change, Q24Hr ± 4Hrs		X	X	X	X	X	X	X	X	X	X					
CRRT Settings and Other RRT Use	X	X	X	X	X	X	X	X	X	X	X	X	X	X	X	X
CRRT Device and SCD Performance	X	X	X	X	X	X	X	X	X	X	X					
Other – Event Driven																
Adverse Events	X	X	X	X	X	X	X	X	X	X	X	X	X	X	X ⁹	X ⁹

¹SCD Treatment Period lasts 240 hours or until termination criteria are met per Section 7

²The Post SCD Period lasts 120 hours or until ICU discharge, whichever comes first

³Window for follow up visits is day from SCD initiation +7 days

⁴Blood for research biomarkers should be completed before SCD initiation (or 6 hours prior), as well as 48h, 96h, 144h, 192h, end of SCD, and 120 hours post SCD \pm 6 hours

⁵Post filter iCa only need recorded in the pre-SCD time period if patient was on CRRT with RCA prior to SCD initiation

⁶Post filter iCa should be obtained Q1Hr \pm 30min until <0.40 mmol/L for two consecutive measurements within the first 12 hours of SCD

⁷Post filter iCa should be obtained Q1Hr \pm 30min until post filter iCa level<0.40 mmol/L for two consecutive measurements after any CRRT recirculation or restart, citrate or calcium rate change, and then Q6Hr \pm 1Hr after

⁸An arterial blood gas is only required if the patient is receiving invasive mechanical ventilation and has an arterial line per standard of care

⁹Only SAEs need to be reported on Day 28 and Day 60

